Pre-Specified Study Protocol and Statistical Analysis Plan

Original Project Title: Comparing the Effectiveness of Fatigue Management Programs for

People with MS

Version date of document: November 01, 2019

Clinical Trial Registration: clinicaltrials.gov #NCT03550170

Funding: This work was supported through a Patient-Centered Outcomes Research

Institute (PCORI) Project Program Award (MS-1610-37015). All statements in this report,

including its findings and conclusions, are solely those of the authors and do not necessarily

represent the views of the Patient-Centered Outcomes Research Institute (PCORI), its Board of

Governors or Methodology Committee.

Method and Analysis

Study Design

We are conducting a randomized clinical trial to directly compare three delivery formats of the *Managing Fatigue* intervention. We are using a pragmatic design approach in which 582 participants with MS are being recruited and randomized to teleconference, internet, or in-person versions of the intervention led by a licensed OT. All versions contain the same intervention content but are presented in ways most appropriate to the delivery format. Our goal is to recruit a diverse research sample to examine the effectiveness of each delivery format on different subgroups of participants (i.e., disease, demographic, and psychosocial characteristics). Outcomes are being measured at baseline, two months, three months, and six months. To help facilitate recruitment, the study is being branded as REFRESH (**RE**ducing **F**atigue and **R**estoring **E**nergy to **S**upport **H**ealth).

Sample Size and Inferiority Margin

A sample size of 582 participants is needed to achieve a power of 0.90 for testing the hypothesis and conducting the moderation analyses. Based on previous studies and to err on the side of being conservative, we assumed an attrition rate of 35%, a standardized mean difference of 0.3, a correlation of 0.45 (rho), and a two-sided alpha level of 0.05. An interaction-to-overall effects ratio estimated the extra number of participants needed to examine interactions between delivery formats and participants' baseline characteristics. The prespecified inferiority margin is ten points, which is based on triangulating anchor-based and distribution-based methods to calculate the minimally important difference (MID) on the Fatigue Impact Scale (FIS), and is consistent with a standardized mean difference of 0.3.3-5

Recruitment and Eligibility

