The primary recruitment method is community outreach in the Midwestern and Northeastern United States, involving four approaches: (1) advertising with non-profit organizations (e.g., visiting support groups and going to events), (2) using social media (e.g., Facebook), (3) asking neurologists and rehabilitation professionals to provide flyers to their patients, and (4) engaging community stakeholders (e.g., snowballing recruitment). Inclusion criteria are a self-reported diagnosis of MS, at least 18 years of age, moderate to severe fatigue (i.e., Fatigue Severity scale score \geq 4),⁶ and ability to speak and read English (i.e., confirmed via phone conversation and self-report). Exclusion criteria are the inability to understand the consent form (e.g., assessed with five questions about the study) or the inability to participate in the intervention (e.g., unwilling or unable to travel outside the home).

Several steps are being taken to ensure that those who meet the study criteria have the opportunity to participate in the intervention: e.g., providing transportation to in-person visits and providing participants with a Chromebook to access the internet intervention if needed. Universal Design Principles for research are also being implemented. For example, recruiting participants through various media (i.e., print, audio, and in-person), providing multiple options to express interest in the study and complete questionnaires (e.g., paper and pencil, internet, and phone), and implementing strategies to include people with low vision (e.g., making reading material available in large-print and audio formats and enabling text-to-speech functionality). Because of the pragmatic design approach, we are monitoring but not excluding participants for receiving other treatments for fatigue or participating in other rehabilitation services before or during the study. Participants are permitted to withdraw from the study at any time for any

reason. Reasons for withdrawal and inability to participate in the intervention are being documented and will be examined in sensitivity analyses.

Randomization and Allocation Concealment

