notify the research office immediately if they suspect an adverse event. The participant's physician is informed when additional services are needed for the treatment of an adverse event. Because it is unlikely that these adverse events will be related to the study protocol, an independent Data and Safety Monitoring Board is not being utilized. If a serious adverse event is related to the protocol, the Institutional Review Board and study sponsor will be notified immediately. Quality control checks (e.g., data generation and attrition rate) will occur throughout the study (i.e., every few months) by the statistician not involved in data collection or delivery of the intervention. Concerns about adverse events or quality control checks will be discussed in the monthly team meetings and conveyed to other stakeholder groups convened during the study, including people with MS.

Data will be downloaded from REDCap into a statistical software program. Linear mixed effects model will serve as the primary analysis tool for examining the differential effects of the intervention delivery format on outcomes. The models will include the group assignment variable, time, and interaction of time and group, as well as the subject-specific random intercept and slope for accounting for individual heterogeneity. Using the fitted model, the trajectory of outcomes will be plotted over the study period. Direct estimates of the treatment effect at specific times will be derived by specifying the least squares means for the Treatment × Time interaction. Noninferiority will be established with a 95% confidence interval (CI) using the prespecified margin of inferiority at each time point, which is set at ten points on the total composite score of the FIS. The prespecified inferiority margin for the Multiple Sclerosis Impact Scale is set at eight points for the physical function subscale and six points for the psychological function subscale. These margins are based on anchored-based methods calculated from previous studies.²⁵ ²⁶

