The purpose of the moderator analysis will be to examine the consistency of the intervention's effect across the following subgroups: (1) disability status (i.e., people with moderate to severe disabilities vs. people with mild impairments, (2) race (i.e., Hispanic and non-whites vs. non-Hispanic whites, (3) environment (i.e., people living in rural areas vs. urban areas), and (4) psychosocial characteristics (i.e., people experiencing societal barriers, depression, low health literacy, low social support, and/or low patient activation vs. people without these characteristics). This analysis will involve adding an additional interaction term of group × time × characteristic and the two-way interaction term of time × characteristic and group × characteristic using the mixed effects model that will be used to detect the main treatment effects on fatigue impact.

The purpose of the mediator analysis will be to examine whether changes in self-efficacy and fatigue self-management behaviors influence the relationship between the interventions and outcomes. Significant changes across time in self-efficacy and fatigue self-management behaviors will be evaluated using the proposed mixed effects analysis. Following Hayes et al.,²⁸ the mediation analysis will involve a series of regression analyses to quantify mediation effects using bias-corrected bootstrapped 95% CI.

We will conduct analyses using both intention-to-treat and per-protocol principles. When using intention-to-treat principles, the treatment of missing values will depend on the type of missingness. In the case of missing at random, the proposed mixed effects models should be sufficient. In the case of missing not at random or non-ignorable, a Bayesian method to jointly model response data and missing data will be applied. When using per-protocol principles, participants who provide complete data and attend four or more intervention sessions will be included in the analysis.

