A series of sensitivity analyses are planned to explore how various assumptions and potential confounders might influence the results. Four pre-specified sensitivity analyses are planned: (1) significant differences in time-varying factors between groups after randomization (e.g., exacerbations, changes in medications, or changes in health and wellness services), (2) assumptions of missing data, (3) differences in prespecified margins, and (4) treatment fidelity measures (e.g., attendance, quizzes, and experience of OT). We plan to examine these factors by comparing adjusted to non-adjusted models. Significant differences in time-varying factors between groups after randomization will be entered into the model as covariates during hypothesis testing. We will examine whether any differences exist in results based on how missing data are treated (e.g., missing at random versus missing not at random). We will also use prespecified margins of 4.8 (i.e., standard error of measurement), 15.5 (the mean of 12 anchoredbased MIDs), and 20 (upper limit of the triangulated anchored and distribution-based MIDs). Last, we will assess whether measures of treatment fidelity, such as OT experience and participants' understanding of material, influence outcomes as well as whether differences exist in the per-protocol analysis when participants who provide complete data and attend all six intervention sessions (compared to four and five of the six sessions) are only included in the analysis.

Public and Patient Involvement

Stakeholder groups comprising individuals with MS, policy advocates, insurance representatives, clinicians, and researchers on the project are informing all aspects of the study. This includes drafting and reviewing recruitment and intervention material, branding of the study, selecting which delivery formats to examine, assessing and finding both the ease and

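### The intention-to-treat missing-data rule switches on MAR versus MNAR, which the data cannot show; it conflicts with the named primary model and leaves open which result decides noninferiority

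*Combined protocol and SAP*

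**What the plan says.** Three paragraphs of the section Data Management and Analysis bear on this.

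- **Model paragraph.** "Linear mixed effects model will serve as the primary analysis tool" for comparing delivery formats. Noninferiority is read from a 95% confidence interval against a margin of ten FIS points at each time point.
- **Intention-to-treat paragraph.** Here "the treatment of missing values will depend on the type of missingness". The two branches are: "In the case of missing at random, the proposed mixed effects models should be sufficient"; and "In the case of missing not at random or non-ignorable, a Bayesian method to jointly model response data and missing data will be applied".
- **Sensitivity paragraph.** "Four pre-specified sensitivity analyses are planned", the second of which concerns assumptions about missing data: "We will examine whether any differences exist in results based on how missing data are treated", with MAR against MNAR given as the example. No condition is attached.

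Elsewhere, Sample Size and Inferiority Margin assumes 35% attrition, described as conservative. Recruitment and Eligibility adds: "Reasons for withdrawal and inability to participate in the intervention are being documented and will be examined in sensitivity analyses".

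The document does not say how, when or by whom the type of missingness will be judged. It gives no form, priors or sensitivity parameters for the joint model, and no rule for the case where the MAR and MNAR results point in different directions.

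**The concern.** MAR and MNAR differ only in whether dropout depends on values that were not observed, once the observed ones are accounted for. No test on the collected data can tell them apart. A rule that selects the analysis on that distinction therefore needs a judgement, and nothing in the plan stops that judgement being made after the results are known.

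This matters more than usual here because the claim is noninferiority. If people who leave a remote format do worse than similar people who stay, and in-person leavers do not, a MAR analysis understates the deficit of the remote format and favours the noninferiority claim. The formats differ a good deal (an asynchronous website, a phone group, tailored individual visits), so dropout related to outcome could differ between arms.

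A single joint model, run once, gives one alternative answer that depends on its own assumptions. It does not tell a reader how much worse the dropouts would have to be to overturn the conclusion.

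**Working it through.** **1. The text.** The plan states no numerical result on this point, so the first check is of the wording.

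| Paragraph | Role of the mixed model | Role of the MNAR analysis | Trigger |
|---|---|---|---|
| Model | primary tool | not mentioned | none |
| Intention-to-treat | used if MAR | replaces it if MNAR | type of missingness |
| Sensitivity | one side of a comparison | other side of the comparison | none |

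The first and third rows fit together: mixed model primary, MNAR as sensitivity. The second does not fit them, because it lets the joint model take over the intention-to-treat analysis. None of the three says which result governs after a disagreement.

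**2. Inputs for an illustration of scale.**

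- From the documents: 582 participants allocated 1:1:1, so 194 per arm; 35% attrition; margin 10 points, stated to be consistent with a standardized difference of 0.3; correlation 0.45; 95% interval.
- Derived: SD = 10/0.3 = 33.3 points.
- Assumed: equal attrition in all arms; completers only; in-person dropouts as MAR predicts; remote-arm dropouts worse than MAR predicts by D points; interval width unchanged by the shift. The 20% attrition rate is added to show the dependence on attrition.

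**3. Tipping point when the MAR estimate is zero.**

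SE = SD × √(2/n), multiplied by √(1 − 0.45²) = 0.893 for baseline adjustment. The shift in the difference is attrition × D. Noninferiority is lost when 1.96 × SE + attrition × D reaches 10, so D = (10 − 1.96 × SE)/attrition.

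| Attrition | n per arm | Adjustment | SE | 1.96 × SE | Tipping D |
|---|---|---|---|---|---|
| 35% | 194 × 0.65 = 126.1 | none | 4.20 | 8.23 | 1.77/0.35 = 5.1 |
| 35% | 126.1 | baseline | 3.75 | 7.35 | 2.65/0.35 = 7.6 |
| 20% | 194 × 0.80 = 155.2 | none | 3.78 | 7.42 | 2.58/0.20 = 12.9 |
| 20% | 155.2 | baseline | 3.38 | 6.62 | 3.38/0.20 = 16.9 |

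**4. Bias of a MAR analysis at a true deficit of 10 points (35% attrition).**

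The false-claim probability at one visit is Φ(0.35 × D/SE − 1.96), against 2.5% with no bias.

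| D | Bias in points | SE 4.20 | SE 3.75 |
|---|---|---|---|
| 5 | 1.75 | 6.1% | 6.8% |
| 10 | 3.50 | 13.0% | 15.2% |
| 15 | 5.25 | 23.9% | 28.8% |

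At 20% attrition and SE 3.78 the figures are 4.5%, 7.6% and 12.2%. All of these describe the MAR mixed model itself, whichever rule led to its use.

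**5. Cost of a free choice between the two analyses.**

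Suppose both analyses are unbiased, each has 2.5% one-sided error, and whichever passes is reported. The error is then 0.05 minus the probability that both pass. With bivariate normal statistics this is 3.2% at an assumed correlation of 0.95 and 3.9% at 0.80. This is the only figure here that relates to the conditional rule, and the correlations are not from the documents.

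**The case against.** The strongest reply is that the plan already has a primary analysis. The model paragraph names the linear mixed model and reads noninferiority from its interval, and the sensitivity paragraph commits to a MAR-versus-MNAR comparison without any trigger. Read together, they make the mixed model primary and MNAR a sensitivity analysis. This stands to the extent that a reader might infer from the intention-to-treat paragraph alone that the deciding analysis is simply left to an untestable trigger, and the section as a whole does not support that. What remains is a conflict: the intention-to-treat paragraph is the specific text on missing values and says that another model will be applied under MNAR, while the sensitivity paragraph promises only to look for differences.

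A reader might also take the 6%, 13% and 24% in step 4 as the damage done by the rule. They are not. They are the bias of the same MAR model that is recommended below as the deciding analysis, under a penalty placed on the remote arms only. If dropouts in both arms were equally worse at equal attrition, the bias would cancel.

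Nor is 35% an expected or observed rate. It is a deliberately conservative planning value, and the plan describes incentives and contact methods to limit attrition. At 20%, the tipping points are more than twice as far away.

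Finally, joint modelling is a recognised MNAR method, and its use is not an error. The gaps are that its form is not fixed and that one fit does not show where the conclusion turns. Documenting reasons for withdrawal helps, but fills neither gap.

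**Conclusion.** The concern holds as a conflict within Data Management and Analysis. The conditional rule cannot be carried out from observed data, it contradicts the named primary model and the untriggered sensitivity comparison, and no text says which result decides if they disagree. That conclusion rests on the wording and needs no assumption.

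Its numerical size is less certain. Reporting whichever analysis passes would raise one-sided error from 2.5% to about 3.2 to 3.9%, but only under assumed correlations of 0.95 to 0.80 and a freedom that the plan does not expressly grant. The tipping points (about 5 to 8 points at 35% attrition, 13 to 17 at 20%) rest on the derived SD of 33.3, completers only, and a one-sided penalty. A mixed model would gain some precision from partial data. They show that the noninferiority conclusion could depend on how dropouts fare, which is a reason to report a tipping point.

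This should be corrected before outcome data are analysed. It does not show that the trial's conclusion would be wrong, and it does not affect the sample size of 582.

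**What to change.** 1. Delete the conditional rule from the intention-to-treat paragraph.
2. State that the linear mixed model under MAR, in all randomized participants as randomized, is the one analysis that decides noninferiority under intention-to-treat.
3. Always report a delta-adjusted tipping-point analysis: impute missing FIS values under MAR, worsen the imputed values in the remote arms by a prespecified range of penalties (for example 0 to 20 points), and give the penalty at which the 10-point conclusion is lost.
4. Keep the Bayesian joint model as a further sensitivity analysis, with its form and priors written down in advance.

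This does not remove MAR bias from the deciding analysis. It fixes in advance which result counts and lets readers judge how far that result depends on the MAR assumption at the attrition actually observed.

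The cost is SAP wording and a few extra imputation runs on data the trial already plans to collect. No participant procedure changes.

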Internet. Similar to the teleconference intervention, the internet intervention lasts for six weeks and is group-based; however, unlike the teleconference intervention, participation is asynchronous, with participants able to log on whenever convenient for them. As per the teleconference program, five to ten participants start the intervention at the same time and interact during the intervention, also facilitated by an OT. Participants are given a username and a password to view the intervention content via a secure website. Each week, a new session is activated. Each session includes content delivered via text and short videos, completion of interactive activities and information sharing. OTs facilitate the group discussion boards by responding to entries, asking questions and prompting discussion, and providing encouragement. Website content can be downloaded by participants who wish to have paper copies. To ensure that all participants are able to access and navigate the site, a welcome week session is delivered prior to the first session. However, no intervention content is delivered during this session.

One-to-one, in-person. Unlike the teleconference and internet interventions, the number and length of sessions for the one-to-one, in-person intervention vary over the six-week period. The OT delivers all six topics, but the pace is tailored to participants' needs and preferences.

Thus, although the topics are consistent, OTs can spend more time on those topics that participants find most relevant to them. The participants and OT are instructed to meet at least three times, with at least seven days between sessions. Similar to the teleconference, participants receive a program manual divided into six sections. Sessions are held at a central location or at participants' homes on a day and time convenient for both the OTs and the participants.

Ensuring the Fidelity of the Interventions

Bellg et al.'s¹⁶ recommendation to monitor all aspects of treatment fidelity are being followed. Our goal is to strike a balance between delivering each format consistently, capitalizing on the unique features of each delivery format, and providing OTs with flexibility to deliver the intervention in a way that meets the participants' needs. This balance is needed to maintain internal validity while helping ensure the generalizability of the intervention when implemented under usual circumstances.

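### The per-protocol rule counts sessions identically in all arms, but in-person sessions vary in number; if a session is a meeting, the reference arm is selected on pacing

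*Combined protocol and SAP*

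**What the plan says.** Data Management and Analysis plans both intention-to-treat and per-protocol analyses and does not say which one decides. For per-protocol, "participants who provide complete data and attend four or more intervention sessions will be included in the analysis". The sensitivity paragraph of the same section repeats the analysis in those who "attend all six intervention sessions (compared to four and five of the six sessions". Neither place gives a version for a particular arm.

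Intervention Procedures describes the formats differently:

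- **Teleconference:** a fixed programme of weekly group calls over six weeks. Staff telephone anyone who misses a call with a shortened summary.
- **Internet:** a new session opens each week for six weeks, and participants log on when they like. A welcome week with no intervention content comes first and is also called a session.
- **One-to-one, in-person (the reference arm):** "the number and length of sessions for the one-to-one, in-person intervention vary over the six-week period". The content, by contrast, is complete for everyone, with only its speed left open: "The OT delivers all six topics, but the pace is tailored to" what the participant needs and prefers. On the number of visits there is a floor: "The participants and OT are instructed to meet at least three times, with at least seven days between sessions". The written material follows the same structure as in another arm: "Similar to the teleconference, participants receive a program manual divided into six sections".

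**The concern.** A count of four, or of six, is a natural exposure threshold where six sessions are scheduled. It is a different kind of threshold where the number of sessions is left to the therapist and the participant. In the in-person arm, a count of meetings measures how the content was spread over visits, not how much content was received.

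Any attendance rule selects on behaviour after randomization, in every arm. The added problem here is that, on the meeting reading, in-person participants who received the whole course are also sorted by how many visits they needed or preferred. The fixed weekly teleconference schedule has no counterpart to that. Because the in-person arm is the reference, it enters both remote-versus-in-person noninferiority comparisons. The per-protocol versions of those comparisons would then set a reference group filtered on pacing against remote groups that are not.

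**Working it through.** The plan states no figure to reproduce. The check applies the written rule to each arm's description under the two possible meanings of *session*.

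**Inputs.** Thresholds of 4 (main) and 6 (sensitivity), from Data Management and Analysis. Teleconference, 6 scheduled sessions; in-person, at least 3 meetings at least 7 days apart with all 6 topics delivered, both from Intervention Procedures.

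**Classification**, assuming complete outcome data, one topic per teleconference session, and make-up calls not counted:

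| Participant | Main set, session = meeting | Six-session set, session = meeting | Main set, session = topic | Six-session set, session = topic |
|---|---|---|---|---|
| In-person, 3 meetings, 6 topics | out (3 < 4) | out (3 < 6) | in | in |
| In-person, 4 or 5 meetings, 6 topics | in | out | in | in |
| In-person, 6 meetings, 6 topics | in | in | in | in |
| Teleconference, 4 of 6 sessions | in | out | in | out |
| Internet | not classifiable | not classifiable | not classifiable | not classifiable |

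The internet row stays open because attendance is not defined for asynchronous use.

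**Feasibility.** With spacing of at least 7 days, k meetings span at least 7(k − 1) days: 3 meetings need 14 days, 4 need 21 and 6 need 35, out of 6 × 7 = 42. Six meetings can therefore be held. The rule is not impossible to meet; it depends on pacing.

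**Which meaning does the text support?**

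- *Meeting.* In the in-person description, sessions vary in number, are spaced in days and have a venue: "Sessions are held at a central location". Content is called topics. Under Ensuring the Fidelity of the Interventions, recordings are made of in-person sessions.
- *Topic or content unit.* The internet description uses the word for a weekly block of content. The sensitivity wording presumes six countable units for everyone, which suits six topics or manual sections and does not suit a variable number of meetings.

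No section states either meaning for the analysis set.

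**Size.** Let s be the share of in-person participants with complete data and all six topics who used exactly three meetings. Let d be the mean Fatigue Impact Scale score of those retained minus that of those excluded. Removing the share s moves the reference mean by d − (1 − s)d = s × d. The documents give neither s nor the size or sign of d. If s = 0 or d = 0, there is no shift. For scale only, on assumed values: s = 0.2 and d = 5 points gives 0.2 × 5 = 1 point; s = 0.6 and d = 5 gives 0.6 × 5 = 3 points. Either could go in either direction, against a margin of 10.

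**The case against.** The strongest reply is that *session* was meant as one of the six topics or manual sections. The internet description and the phrase about four and five out of six both point that way, and every arm has six such units. This stands as a live reading. A reader might infer that the plan certainly excludes in-person participants who followed the delivery instruction, but the documents do not settle that. They do use the word for meetings in the description of the very arm affected, so the topic reading cannot simply be assumed.

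Second, three meetings is a floor for delivery, and a plan may set its per-protocol exposure threshold higher. That is legitimate, and it means that four of six scheduled sessions and three of a minimum of three are not shares of the same thing. But the plan does not say that it intends this, and where all six topics are delivered whatever the number of visits, a higher meeting count does not mean more content.

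Third, the plan intends adjusted and unadjusted models for "treatment fidelity measures (e.g., attendance, quizzes, and experience of OT". This is partial mitigation. It would show some sensitivity to attendance, but it does not return excluded participants to the per-protocol set.

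Finally, a reader might attach a loss of power to the exclusions. The documents do not support one. The stated power of 0.90 belongs to 582 participants and to the hypothesis test and moderation analyses; no power is stated for the per-protocol set.

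**Conclusion.** The point holds as a conflict between the per-protocol rule and the description of the in-person arm, and it should be fixed. It is clear that the rule uses an undefined unit, that one count is applied to formats with different structures, and that attendance has no meaning yet for the internet arm. The exclusion of in-person participants who received all topics, and hence selection of the reference arm on pacing, follows only if a session is a meeting.

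The intention-to-treat analysis is untouched, and per-protocol is not named as the deciding analysis. How many participants are affected is unknown and could be close to none. A reader might infer that the rule tilts the comparison towards or away from noninferiority; nothing in the documents shows a direction. The shifts shown above rest wholly on assumed inputs and are not estimates.

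**What to change.** Reconcile the in-person description with the two per-protocol statements before outcome data are seen:

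- Define per-protocol in every arm by content received in the assigned format, at the plan's own thresholds: complete data and at least four of the six topics in the main set, all six in the sensitivity set. Add no meeting-count condition for the in-person arm, since that would bring back a hurdle for the reference arm alone.
- State what *session* and *attend* mean in each arm, including that the internet welcome week does not count as content.
- Derive topic receipt from therapist notes, session checklists and individual attendance for teleconference and in-person, and from web logs for internet. State in advance how teleconference make-up calls and internet page visits count.
- Report the number excluded per arm under each rule and the distribution of in-person meetings.

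The cost is SAP wording, programming and some abstraction. The fidelity section already plans notes with time per topic, checklists, attendance, and log-in and page counts, but does not say that topic receipt is a structured field or what the checklists contain. Therapists cannot be masked, so abstraction rules must be fixed in advance. Teleconference notes may describe the group and would need joining to individual attendance. Page visits show access rather than full receipt. The change concerns the analysis set only; delivery of the intervention stays as it is.
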